# List of abbreviations

**ABR** annualised bleeding rate

ΑE adverse event

aPTT activated partial thromboplastin time

AT antithrombin

maximum plasma concentration  $C_{\text{max}}$ 

**CPoC** clinical proof of concept

the name 'eptacog alfa (rFVIIa)' will be used throughout

the document and the product is identical to eptacog alfa

rFVIIa, 'NovoSeven®, and 'NiaStaseRT®',

FAS full analysis set

FVIIa activated coagulation factor VII

Hemo-TEM Hemophilia Treatment Experience Measure

i.v. intravenous(-ly)

MAR missing at random

MedDRA Medical Dictionary for Regulatory Activities

PD pharmacodynamics

PGI-C Patient's Global Impression of Change

PK pharmacokinetics 
 Statistical Analysis Plan
 Date:
 23 October 2018
 Novo Nordisk

 Trial ID: NN7415-4310
 Version:
 1.0

 UTN: U1111-1179-2925
 Status:
 Final

 EudraCT No.: 2016-000510-30
 Page:
 4 of 16

PRO patient reported outcome

PT prothrombin time

s.c. subcutaneous(-ly)

SAS safety analysis set

SDS Sheehan Disability Scale

SF-36v2 36-Item Short Form Health Survey

SIAQ-ISRQ Injection Site Reaction Questionnaire domain of Self-

Injection Assessment Questionnaire

TEAE treatment emergent adverse events

TFPI tissue factor pathway inhibitor

TSQM Treatment Satisfaction Questionnaire for Medication

VERITAS-PRN® Validated Hemophilia Regimen Treatment Adherence

Scale

CONFIDENTIAL

Date: Version: Status: Page:

23 October 2018 | Novo Nordisk 1.0 Final 5 of 16

### 1 Introduction

#### 1.1 **Trial information**

NN7415-4310, explorerTM4, is a multicentre, randomised, open-label, controlled trial where daily treatment with concizumab is evaluated against on-demand treatment in a population of Haemophilia A and B patients with inhibitors. For further information about the trial please refer to the protocol.

#### 1.2 Scope of the statistical analysis plan

This Statistical Analysis Plan (SAP) is based on the protocol A Multi-Centre, Randomised, Open-Label, Controlled Trial Evaluating the Efficacy and Safety of Prophylactic Administration of Concizumab in Haemophilia A and B Patients with Inhibitors, version 3, and amendments 1 and 2.

The scope of this SAP is to specify some further technical details on matters which have not been adequately described in the protocol. No changes have been made to the analyses specified in the protocol.

### 2 Statistical considerations

All endpoints referring to the time frame of at least 24 weeks will be evaluated in the main part of the trial, defined to end when the last patient has completed a minimum of 24 weeks of treatment or at LPFT (visit 2) + 24 weeks if the last patient has withdrawn before visit 9. Please refer to Figure 2–1 for further information.

Data from when the on-demand treated patients are transferred to concizumab subcutaneous (s.c.) prophylaxis will not be included in this evaluation. Observations from the extension part in the ondemand arm will be summarised separately as well as combined with observations from the main part when reporting the extension part data.

Endpoints comprising number of bleeding episodes will be evaluated based on treated bleeding episodes only. Multiple bleeding locations occurring from the same event (e.g., due to a bicycle accident) or at the same time point will be counted as one bleeding episode. Further, the endpoints will not include re-bleeds.

A re-bleed is defined as a bleeding episode (worsening of bleeding site conditions e.g. swelling, pain) within 72 hours after stopping treatment of a previous bleeding episode at the same (or subset of the same) anatomical location. If a bleeding episode occurs in the same location 72 hours after stopping treatment, the bleed is defined as a new bleeding episode.

CONFIDENTIAL

Date: Version: Status: Page:

23 October 2018 | Novo Nordisk 1.0 Final 6 of 16

# Clinical proof of concept

The statistical analysis of the collected data aims to establish clinical proof of concept (CPoC) that concizumab is efficacious in preventing bleeding episodes in haemophilia patients with inhibitors. The objective will be assessed when the last of the 24 patients has completed 24 weeks of dosing (or has withdrawn before that).

Two criteria will be evaluated in a hierarchical fashion in support of CPoC comprising a comparison of the annualised bleeding rate (ABR) of all patients in the concizumab group, irrespective of individual dose titration, with the ABR of the patients in the on-demand arm using different sets of observations. The primary CPoC criterion aims at evaluating the effect of concizumab when given at the last dose level reached for the patient. Hence, for this evaluation, only observations from the period where patients are on their end dose at time of analysis will contribute to the analysis. Furthermore, observations from the 2 week run-in period will not be included. Since this evaluation disregards a subset of data collected post randomisation, the result should be viewed taking into account the potential bias. The second CPoC criterion aims at evaluating the effect of concizumab when given as an escalation regimen. Hence, this will compare the ABR of patients in the concizumab arm with the ABR of the patients in the on-demand arm using all data collected after randomisation. The second CPoC criterion will only be evaluated if the first one succeeds.

The referred comparisons will be made using a negative binomial model with log of exposure time in main part as offset and regimen as factor (concizumab vs. on-demand). For each criterion, evidence of effect will be concluded if the 95% confidence interval of the treatment ratio is below 1.

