#### 2.1 Sample size calculation

The estimand will be defined as the "if all patients had adhered" estimand.

The treatment ratio between prophylactic s.c. concizumab and on-demand intravenous (i.v.) eptacog alfa (rFVIIa) during at least 24 weeks for all randomised patients if all patients adhered to trial drug and did not initiate alternative treatment options.

Statistical Analysis Plan	CONFIDENTIAL	Date:	23 October 2018	Novo Nordisk
Trial ID: NN7415-4310		Version:	1.0	
UTN: U1111-1179-2925		Status:	Final	
EudraCT No.: 2016-000510-30		Page:	7 of 16	

This estimand is a de jure estimand assessing the expected added benefit a patient can achieve if continuing treatment with prophylactic s.c. concizumab as compared to on-demand i.v. eptacog alfa (rFVIIa) under similar conditions as observed in this trial.

The sample size calculation has been determined based on this estimand and the CPoC criteria taking the small patient population into account, while also aiming for an acceptably narrow 95% confidence interval for the rate ratio.

Sufficient inference on bleeding episodes for the primary CPoC criterion is judged to be accommodated by 16 patients in the concizumab arm and 8 in the comparator arm. It is expected that the treatment duration of the main part allowing for escalation time for some patients is on average 6 months in the below calculations.

When evaluating the power of the negative binomial analysis referred above, annual bleeding rates of 24 and 6 are assumed for the on-demand patients and the end dose concizumab regimen, respectively. Assuming further over-dispersion of 7, the power for concluding superiority of the concizumab regimen becomes approximately 80%. The power under varying values of true ABR and over-dispersion for the primary CPoC criterion are shown below in Table 2–1.

Table 2-1 Power in superiority comparison between concizumab prophylaxis and on-demand treatment under different assumptions of ABR for concizumab and overdispersion (assuming on-demand ABR=24).

Power	Over-dispersion (over 6 months)			
ABR (concizumab)	6 7 8			
6	89%	82%	75%	
7	84%	75%	70%	
8	77%	69%	66%	

For the secondary CPoC criterion that includes data prior to potential dose escalation, it is expected that the treatment duration of the main part is on average 8 months with an average ABR of 7.6 for the concizumab regimen. This yields a marginal power of approximately 70% for the secondary CPoC criterion.

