### 2.3.1 Estimand and primary statistical analysis

The estimand for the primary endpoint is the "if all patients had adhered" estimand.

The treatment ratio between prophylaxis s.c. concizumab and on-demand i.v. eptacog alfa (rFVIIa) during at least 24 weeks for all randomised patients if all patients adhered to trial drug and did not initiate alternative treatment options. To initiate alternative treatment options in this respect is defined as stopping concizumab or eptacog alfa on-demand treatment and initiating alternative treatment options.

This estimand is a de jure estimand assessing the expected added benefit a patient can achieve if continuing treatment with prophylactic s.c. concizumab as compared to on-demand i.v. eptacog alfa (rFVIIa) under similar conditions as observed in this trial.

The estimand for the primary endpoint will be estimated using negative binomial regression with log of exposure time in the included observational period of the main part as offset and regimen as factor. The offset for first CPoC criterion of patients in concizumab arm is the log of the individual exposure time at the last dose level reached at the time of analysis excluding the 2 weeks run-in period for subjects on 0.15 mg/kg. The offset for the second criterion of patients in concizumab arm is the log of the individual exposure time in the main part. For patients in the on-demand arm regardless of criterion, the offset is the log of the exposure time in the main part. The analysis provides an estimate of the ABR ratio between regimens (concizumab prophylactic and on-demand eptacog alfa (rFVIIa)) with corresponding 95% confidence interval and also actual estimate of the ABR with corresponding 95% confidence interval for each regimen. This analysis has the underlying assumption that the missing data mechanism is "missing at random", i.e. missing at random (MAR). Under this assumption, the statistical behaviour of the missing data (given the

CONFIDENTIAL

Date: Version: Status: Page:

23 October 2018 | Novo Nordisk 1.0 Final 9 of 16

observed responses and the mean value structure) is assumed to be the same as for the observed data. The estimand will be estimated based on the FAS and only data collected prior to discontinuation of trial product or initiation of alternative treatment options will be used to draw inference.

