## 2.4 Supportive secondary endpoints

# 2.4.1 Supportive secondary efficacy endpoints

- The number of bleeding episodes during 76 weeks from treatment onset
- The number of spontaneous bleeding episodes during at least 24 weeks from treatment onset
- The number of spontaneous bleeding episodes during 76 weeks from treatment onset

The number of spontaneous bleeding episodes during at least 24 weeks from treatment onset will be addressed in terms of the same estimand as for the primary endpoint. The estimand will be estimated using the same negative binomial regression model as for the primary endpoint and performing the same two analyses as for the primary endpoint; one only including observations from the period on the last dose level for patients treated with concizumab and one including the entire escalation regimen.

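### Must the plan name the type of 95% interval, or add a small-sample correction, before proof of concept is judged on 16 against 8 patients?

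*SAP*

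**What the plan says.** The SAP's section on clinical proof of concept compares the arms with a "negative binomial model with log of exposure time in main part as offset and regimen as factor (concizumab vs. on-demand") and applies one rule to both criteria: "evidence of effect will be concluded if the 95% confidence interval of the treatment ratio is below 1". Section 2.3.1 repeats the model ("The estimand for the primary endpoint will be estimated using negative binomial regression with log of exposure time") and promises a ratio with a 95% confidence interval: "The analysis provides an estimate of the ABR ratio between regimens". For the first criterion the concizumab offset is "the log of the individual exposure time at the last dose level reached at the time of analysis", without the run-in period. Section 2.4.1 reuses the model for spontaneous bleeds: "The estimand will be estimated using the same negative binomial regression model as for the primary endpoint".

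Section 2.1 judges the inference to be "accommodated by 16 patients in the concizumab arm and 8 in the comparator arm". With annual rates of 24 and 6 and over-dispersion 7, it says that "the power for concluding superiority of the concizumab regimen becomes approximately 80"%; Table 2-1 prints 82% for that cell.

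None of these sections names the interval type, the reference distribution or a small-sample adjustment. Sections 3.4 and 3.5, which clarify the offset and the sensitivity analyses, do not either.

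**The concern.** The interval is both the decision rule and the reported measure of precision, and the smaller arm has eight patients. Two things make a standard likelihood-based interval too narrow here. Maximum likelihood tends to underestimate the dispersion, and the normal or chi-square quantile treats that estimate as known. If the shortfall were large, proof of concept would be declared too often and the reported interval would overstate precision. Leaving the type open in an open-label trial also leaves a choice that could, in a borderline case, be made after the data are seen.

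**Working it through.** **Inputs from the SAP.** 16 and 8 patients; annual rates 6 and 24; average 6 months, so expected counts per patient of 3 and 12; over-dispersion 7 (section 2.1).

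**Assumption.** Over-dispersion is read as variance divided by mean over the period. At a mean of 12 the negative binomial dispersion is k = (7 - 1)/12 = 0.5.

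**The plan's own figure.** Var(log ratio) = 7/(8 × 12) + 7/(16 × 3) = 0.0729 + 0.1458 = 0.2188, so SE = 0.468. Then log(24/6)/SE = 1.386/0.468 = 2.96, and 2.96 - 1.96 = 1.00, which gives power of about 84%. Simulation is more exact. With gamma-Poisson counts and a maximum likelihood fit with common dispersion, power is 81.8-82.6% with Wald and 80.7-81.4% with profile likelihood, against the printed 82%. Over the nine cells of Table 2-1 the mean gap is 1.3 points for Wald, 1.6 for the likelihood ratio and 3.5 for t on 22 degrees of freedom. The table therefore does not separate the first two types, and fits the t interval less well.

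**Why coverage falls short.** With rate 24 in both arms, the variance is (1/12 + 0.5) × (1/8 + 1/16) = 0.1094. The mean fitted k is about 0.46, not 0.50. Putting 0.46 in gives 0.1019, so the SE is too small by a factor √(0.1019/0.1094) = 0.965. That alone would bring 95% coverage down to about 94%; the variability of the estimated k adds to the shortfall.

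**Size at the null.** Rate 24 in both arms, 6 months, over-dispersion 7; 60,000 simulated trials:

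| Interval | Coverage | Wholly below 1 | Wholly above 1 |
|---|---|---|---|
| Wald | 92.4% | 3.3% | 4.3% |
| Profile likelihood | 93.6% | 3.0% | 3.4% |
| Wald SE with t(22) = 2.074 | 93.9% | 2.6% | 3.5% |

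False success exceeds the implied 2.5% by 0.8, 0.5 and 0.1 points. More of the missed coverage lies above 1, where no success is claimed.

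**Range over ten null settings.** These use rates of 6, 12 or 24, k of about 0.4 to 2, 6 or 8 months, and some unequal exposure times, which are assumed.
- Wald: coverage 91.4-92.9%, false success 2.9-3.4%.
- Profile likelihood: 92.9-93.9% and 2.7-3.1%.
- t(22): 92.9-94.2% and 2.3-2.7%.

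A further run at rate 6 with k = 2 gave Wald false success of 3.5%, so about 1 point is the outer limit. For the second criterion (8 months, k = 0.5) Wald gives 92.6% and 3.2%.

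**Size at the planned effects.** Over the nine Table 2-1 cells coverage is about 92-94% for Wald and 94-95% for both profile likelihood and t(22). The least favourable result, about 90% for Wald, came at rates 24 against 6 with assumed unequal exposures and k = 2.

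**Cost of the correction.** At the planning case power is 82.6% (Wald), 81.4% (profile) and 79.4% (t). The t interval loses 3.2 points against Wald (2.6-4.0 over the table) and 2.0 against profile likelihood. With SE 0.468, an estimated ratio of 0.25 would have the interval 0.25 × exp(±1.96 × 0.468) = 0.10 to 0.63 with the normal quantile, and 0.25 × exp(±2.074 × 0.468) = 0.09 to 0.66 with t.

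**The case for a change.** The best case for acting is that the SAP says it exists to add technical detail, the interval type is such a detail, and here it is the whole decision rule. Section 2.1 also names an acceptably narrow interval as a design aim, and an interval that is narrow partly because it under-covers does not truly meet that aim. Naming the type costs one sentence. In about 1 to 3 planning-case trials in 100, the verdict would differ between Wald and one of the other two intervals.

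What stands: the type is not named, the under-coverage is real, and naming the type in the analysis program specification before the data are seen is good practice.

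What does not stand: the text leaves a correction unstated, which does not show that none will be used, and section 3.4 places the model in a protocol section that is not at hand. The lower coverage ranges come from settings with no effect; at the planned effects profile likelihood is close to nominal. The t quantile is not a clear improvement either. It gains about 0.3-0.5 points of coverage over profile likelihood at the null with rate 24 and essentially nothing at the Table 2-1 effects, still falls 1-2 points short of 95% at the null, and costs more power.

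**Conclusion.** No change to the plan is needed. A 95% confidence interval from a negative binomial regression is an ordinary specification, and either usual reading leads to a sound proof-of-concept conclusion. False success rises by about 0.2-0.9 points over an implied 2.5% that the SAP does not itself state, and about 80% power holds for both. The second criterion is tested only after the first succeeds, so the hierarchy adds no inflation when neither null is false. The remaining effect is a reported interval that is slightly too narrow, mostly under Wald. Removing part of that with a t quantile trades about 3 points of power for a partial gain, and with so few patients a sponsor statistician could fairly decline it.

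This rests on the reading of over-dispersion as variance over mean, which reproduces Table 2-1 closely, and on the assumed ranges of k and exposure times. Much greater dispersion together with very uneven exposure would make the Wald shortfall larger.

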### Clinical arguments for the hierarchical test approach

Concizumab exhibits non-linear pharmacokinetics (PK) due to target mediated drug disposition and it is expected that the dose response curve of the ABR is rather steep. This implies that patients that are on a dose which is not efficacious are likely to bleed as patients that are not treated at all. The subset of data collected from the last dose clinically deemed as efficacious would reflect the efficacy of concizumab in the given patient.

#### 2.1 Sample size calculation

The estimand will be defined as the "if all patients had adhered" estimand.

The treatment ratio between prophylactic s.c. concizumab and on-demand intravenous (i.v.) eptacog alfa (rFVIIa) during at least 24 weeks for all randomised patients if all patients adhered to trial drug and did not initiate alternative treatment options.

Statistical Analysis Plan	CONFIDENTIAL	Date:	23 October 2018	Novo Nordisk
Trial ID: NN7415-4310		Version:	1.0	
UTN: U1111-1179-2925		Status:	Final	
EudraCT No.: 2016-000510-30		Page:	7 of 16	

This estimand is a de jure estimand assessing the expected added benefit a patient can achieve if continuing treatment with prophylactic s.c. concizumab as compared to on-demand i.v. eptacog alfa (rFVIIa) under similar conditions as observed in this trial.

The sample size calculation has been determined based on this estimand and the CPoC criteria taking the small patient population into account, while also aiming for an acceptably narrow 95% confidence interval for the rate ratio.

Sufficient inference on bleeding episodes for the primary CPoC criterion is judged to be accommodated by 16 patients in the concizumab arm and 8 in the comparator arm. It is expected that the treatment duration of the main part allowing for escalation time for some patients is on average 6 months in the below calculations.

When evaluating the power of the negative binomial analysis referred above, annual bleeding rates of 24 and 6 are assumed for the on-demand patients and the end dose concizumab regimen, respectively. Assuming further over-dispersion of 7, the power for concluding superiority of the concizumab regimen becomes approximately 80%. The power under varying values of true ABR and over-dispersion for the primary CPoC criterion are shown below in Table 2–1.

Table 2-1 Power in superiority comparison between concizumab prophylaxis and on-demand treatment under different assumptions of ABR for concizumab and overdispersion (assuming on-demand ABR=24).

Power	Over-dispersion (over 6 months)			
ABR (concizumab)	6 7 8			
6	89%	82%	75%	
7	84%	75%	70%	
8	77%	69%	66%	

For the secondary CPoC criterion that includes data prior to potential dose escalation, it is expected that the treatment duration of the main part is on average 8 months with an average ABR of 7.6 for the concizumab regimen. This yields a marginal power of approximately 70% for the secondary CPoC criterion.

In prior Novo Nordisk trials conducted in haemophilia patients, the typical 1-year over-dispersion for non-inhibitor patients on prophylaxis with coagulation factor FVIII or coagulation factor IX has been in the range 4-8, implying 24 weeks over-dispersion of 3-5 (e.g. in NN7008-3543, NN7088-3859 and NN7999-3747). In the NN7128-1907 trial in inhibitor patients, larger 1-year overdispersion values of approximately 21 and 18, respectively, were observed during an initial 3-month on-demand period and a subsequent 3-month prophylaxis period. It is expected that the variation in the current trial will be smaller, partly due to the longer duration of the trial and partly due to an expected more homogenous patient population. Another published trial including inhibitor patients,

Statistical Analysis Plan	CONFIDENTIAL	Date:	23 October 2018	Novo Nordisk
Trial ID: NN7415-4310		Version:	1.0	
UTN: U1111-1179-2925		Status:	Final	
EudraCT No.: 2016-000510-30		Page:	8 of 16	

comparing prophylaxis using FEIBA® with on-demand treatment, showed 6-month over-dispersion of 4-5 . On that background, an over-dispersion of 7 over the 24 weeks in main part of the current trial is deemed realistic.

# 2.2 Definition of analysis sets

All dosed patients will be included in the Full Analysis Set (FAS) as well as in Safety Analysis Set (SAS).

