## 2.5 Interim analysis

The trial does not include a formal interim analysis. However, the split of the trial into a main and extension part offers the opportunity of reporting results before the end of the trial. For patients in

Statistical Analysis Plan		Date:	23 October 2018	Novo Nordisk
Trial ID: NN7415-4310	CONFIDENTIAL	Version:	1.0	
UTN: U1111-1179-2925	CONFIDENTIAL	Status:	Final	
EudraCT No : 2016-000510-30		Page.	13 of 16	

the concizumab s.c. prophylaxis arm, main part is defined to end when the last patient has completed a minimum of 24 weeks of treatment or at LPFT (visit 2) + 24 weeks if the last patient has withdrawn before visit 9. For patients in the on-demand arm, the main part consists of observations from randomisation until transfer to concizumab s.c. prophylaxis treatment or withdrawal from trial, whichever comes first. All observations for these patients after transfer to concizumab treatment is regarded as extension part of the trial. Other reporting of the trial might be done during the extension part once the data collection and review of the main part data has been finalised and individual clinical trial reports might in such case be issued. A clinical trial report describing results from the main and the extension part will be written when the last patient has either completed or withdrawn from the trial. All main conclusions regarding clinical proof of concept and dose guidance for phase 3 will be based on the reporting after the main part, see Figure 2–1.

[figure not shown]

Figure 2–1 Definition of main and extension part

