### 3.4 Offset definition for negative binomial regression for primary endpoint

Section 17.3.1 of the protocol defines the offset of the negative binomial regression as log of exposure time in the main period. For patients in the concizumab arm, this definition only accounts for the second CPoC criterion. The offset should reflect the observation period which differs for subjects in the concizumab treatment arm for the first CPoC which has been further clarified in section 2.3.1 of this document.

Section 17 of the protocol describes that the CPoC will be evaluated in a hierarchical fashion using two criteria to evaluate the effect of concizumab. The first CPoC criterion is evaluated using only a subset of observations where concizumab patients are at the last dose level reached at the time of analysis and excluding observations from the 2 weeks run-in period with 0.15 mg/kg. The second CPoC criterion is evaluated using all observations in the main part after randomisation.

The offset for first CPoC criterion of patients in concizumab arm is the log of the individual exposure time at the last dose level reached at the time of analysis excluding the 2 weeks run-in period for subjects on 0.15 mg/kg. The offset for the second criterion of patients in concizumab arm is the log of the individual exposure time in the main part. For both criteria and patients in the ondemand arm, the offset is the log of the exposure time in the main part.

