#### 3.8 **Definition of TEAE**

In section 17.4.2 a TEAE is defined as "an event that has onset from the first exposure to treatment until the last visit in the trial." Since the trial design is concizumab s.c. prophylaxis with on-demand treatment of bleeds with eptacog alfa versus placebo with on-demand treatment of with eptacog alfa then first exposure for the eptacog alfa on-demand arm is actually at randomisation. To treat each arm similarly TEAE is defined as an event that has onset after randomisation as defined in section 2.4.2 of this document.

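### Could defining the analysis sets as dosed patients drop bleed-free patients from the on-demand arm?

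*SAP*

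**What the plan says.** Section 2.2 is a single sentence: "All dosed patients will be included in the Full Analysis Set (FAS) as well as in Safety Analysis Set (SAS". Section 2.3.1 then ties the primary estimate to that set: "The estimand will be estimated based on the FAS and only data collected prior to discontinuation of trial product". Section 2 restricts the bleeding endpoints to treated bleeds: "Endpoints comprising number of bleeding episodes will be evaluated based on treated bleeding episodes only".

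Other sections describe when time starts to count in the on-demand arm:

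- Section 3.8, explaining the definition of treatment-emergent events, says that "first exposure for the eptacog alfa on-demand arm is actually at randomisation".
- Section 2.5 says that for this arm "the main part consists of observations from randomisation until transfer to concizumab s.c. prophylaxis treatment or withdrawal from trial, whichever comes first".
- Section 2.3.1 sets the model offset: "For patients in the on-demand arm regardless of criterion, the offset is the log of the exposure time in the main part".
- Section 3.4 says: "The second CPoC criterion is evaluated using all observations in the main part after randomisation".

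Section 3.9 mentions eptacog alfa given at visits 3 and 9.1 but does not say to which arm.

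**The concern.** For daily concizumab, being dosed has an obvious meaning. For on-demand eptacog alfa it does not, because the drug is given in response to the event that the endpoint counts. If dosed means having received eptacog alfa, entry to the analysis set depends on having bled. An on-demand patient who withdraws bleed-free before transfer to concizumab would contribute neither a zero count nor exposure time. A concizumab patient might also go undosed, but not for lack of bleeds. The exclusion would therefore act on one arm, raise its annualised bleeding rate (ABR) and move the ratio in favour of concizumab. With 8 comparator patients, one exclusion would be visible in the estimate, and the on-demand safety denominator would lose the same patient.

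**Working it through.** **1. What the sections settle.** Only section 3.8 speaks directly to first exposure in the on-demand arm, and it answers randomisation. Section 2.5 defines an observation window that opens at randomisation, and section 2.3.1 makes that window the offset. Under these two sections every randomised on-demand patient has exposure time whether or not a bleed occurred. The proof-of-concept text in section 2 and section 3.4 say which observations enter the second criterion. They do not define set membership, but they fit the same reading. No section supports entry at the first eptacog alfa injection.

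**2. Planning model.** Inputs from section 2.1: 16 and 8 patients, ABR 6 and 24, over-dispersion (variance/mean) 7, average 6 months. Expected bleeds are 16 × 3 = 48 and 8 × 12 = 96. Then SE(log ratio) = √(7/48 + 7/96) = 0.468, and power is Φ(1.386/0.468 − 1.96) ≈ 84%. Simulating 4,000 trials with a negative binomial fit gives 82.2%, against 82% in Table 2–1, so the model matches the plan's own.

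**3. How likely is a bleed-free leaver?** The gamma shape is k = 12/(7 − 1) = 2. The chance of no treated bleed by week t is [2/(2 + 24t/52)]². The withdrawal weeks are assumed; the SAP gives none.

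**4. Effect of dropping one.** Take seven on-demand patients with 12 bleeds in 26 weeks and one with none in t weeks, k fixed at 2. The fitted rate λ solves 7(12 − 0.5λ)/(1 + 0.25λ) = λs/(1 + 0.5λs), with s = t/52. Without the leaver λ = 24 and the ratio is 6/24 = 0.250.

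| Leaves at week | P(no bleed) | ABR, leaver kept | Rise if dropped | Ratio, leaver kept |
|---|---|---|---|---|
| 2 | 47% | 22.83 | 24/22.83 = +5% | 0.263 |
| 4 | 27% | 22.27 | +8% | 0.269 |
| 8 | 12% | 21.70 | +11% | 0.276 |
| 12 | 7% | 21.42 | +12% | 0.280 |

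Using 24 weeks for the seven completers gives nearly the same rates (22.82, 22.25, 21.68, 21.39). With the dispersion estimated instead of fixed (3,000 simulated trials per week), the median rise is 7%, 10%, 12% and 13%.

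**5. Effect on the conclusion.** With seven on-demand patients, SE = √(7/48 + 7/84) = 0.479, so the upper limit factor is exp(1.96 × 0.479) = 2.56. The upper limit is about 0.250 × 2.56 = 0.64 with the leaver dropped. Applying the same factor with a week-12 leaver kept gives about 0.280 × 2.56 = 0.72. Both are below 1.

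In the simulated trials of step 4, dropping the leaver moved the upper limit from at or above 1 to below 1 in 3.6%, 5.0%, 7.1% and 8.8% of trials (weeks 2, 4, 8, 12), and never the reverse. The chance that at least one of 8 leaves bleed-free is 1 − (1 − w·P)⁸, where w is the proportion leaving and P the chance of no bleed:

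- w = 5%: 17.3%, 10.3%, 4.8%, 2.8%
- w = 10%: 31.9%, 19.7%, 9.5%, 5.5%

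Multiplying by the rates above gives between 2.8% × 8.8% = 0.2% and 31.9% × 3.6% = 1.1%. This already supposes that the literal reading is used and that the leaver received no eptacog alfa.

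**The case for a change.** The best case for a change is that probable intent is not a definition. Section 3.8 was written for adverse events and is not carried into section 2.2. The sponsor saw there that the two arms needed a common starting point, yet left the analysis sets alone. Taken literally, a patient could have a treatment-emergent event under section 2.4.2 and still fall outside the safety set. The trial is open-label with 8 comparator patients, so membership should not be open to debate once bleed counts are known. The possible bias has one direction.

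What stands is that section 2.2 is loosely worded and that the direction is as described. The rest carries less weight. The sections that clash with the literal reading are themselves the evidence against adopting it. To exclude a randomised on-demand patient with main-part time, an analyst would have to set aside sections 2.5 and 3.8, which were fixed in the same final document. Section 2.4.2 lists all adverse events, so an early event would still be seen. What counts as dosing in this arm, and who receives eptacog alfa at visit 3, are also matters commonly left to the protocol, which is not at hand. If on-demand patients are dosed at visit 3, only those leaving before that visit could be affected.

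**Conclusion.** No change is called for. Section 2.2 omits a detail that the rest of the SAP supplies: on-demand patients count from randomisation. The sample size and the 82% power are unaffected. A biased result would need the literal reading, an early bleed-free withdrawal and no eptacog alfa by any other route, all at once. If that happened to one patient of 8 at weeks 2 to 12, the on-demand ABR would be overstated by about 5% to 12% with fixed dispersion, or 7% to 13% with it estimated. At the planning ratio the upper confidence limit would stay well below 1 with or without that patient. The chance of a changed first-criterion conclusion, about 0.2% to 1.1%, rests on the planning values and on an assumed 5% to 10% early withdrawal; a higher rate would raise it.
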